### **7.2 Screening (Visit 1)**

The purpose of this visit is to determine study eligibility and may be conducted over multiple days. Potential participants and their study partners must sign an informed consent form and HIPAA Authorization prior to administration of any study-related procedures. After consent is obtained, participants will be given the MMSE, the CDR and Logical Memory (Delayed Paragraph Recall from the Wechsler Memory Scale–Revised) to determine study eligibility.

In addition, information regarding demographics, concurrent medications, medical history and adverse events will be gathered from the participant and study partner. Vital signs, height and weight will be measured. A brief physical and neurological examination (which include a nasal examination), Modified Hachinski scale and a standard 12-lead resting ECG will be performed. The ECG report will be reviewed, signed, and dated by the investigator or a medically qualified staff member as delegated by the Principal Investigator. Those with clinically significant ECG findings will be referred for follow-up as deemed appropriate by the investigator.

Blood will be drawn and a urine sample obtained for routine clinical laboratory evaluations. If values are outside of the laboratory’s normal range and determined clinically significant by the investigator, lab tests may need to be repeated and may be considered exclusionary for

participation in the study. Blood samples will also be collected for ApoE genotyping and optional DNA storage.

A screening MRI scan will be conducted for participants who met eligibility criteria (as determined by the site investigator). A local clinical read of the MRI will be reviewed by the site principal investigator (or appropriately delegated staff member) for eligibility. If the participant continues to meet all inclusion and exclusion criteria and no safety concerns are identified from the MRI, the participant can proceed to the baseline visit after approval by a clinical monitor.

Prior to randomization, the Project Director must approve any exceptions or questions regarding possible exclusionary medications, medical conditions, or laboratory tests. Re-screen is allowed, should the original screen be a failure. The re-screen should typically occur more than 3 months after the original screen failure.

### 7.3 Baseline (Visit 2)

Results from all screening procedures must be reviewed and all inclusion/exclusion criteria must be met prior to proceeding to baseline. Baseline visit will be scheduled 2-4 weeks after the screening visit. If the baseline visit is scheduled out-of-window (more than 4 weeks from screening), approval to proceed to the baseline visit should be obtained from the project director and a rescreen may be required. The baseline procedures may be completed over multiple days, but all assessments should be completed within seven days.

Vital signs and weight will be obtained, a nasal examination will be performed and concurrent medications and adverse events will be documented.

Blood for plasma biomarkers will be collected immediately before participants undergo the optional lumbar puncture. Plasma insulin, glucose, A $\beta$ 40 and A $\beta$ 42 should be measured in the morning after an overnight fast, if possible. Additional plasma, along with serum and peripheral blood mononuclear cells (PBMCs) will be collected and banked.

Cognitive and behavioral assessments will be performed and study procedures will be standardized such that the ADAS-Cog12 will be given first. Additional assessments include a memory composite (Story Recall and FCSRT), an executive function test (Trail-making Test), the ADCS-MCI-ADL and the Neuropsychiatric Inventory (NPI). A Research Satisfaction Survey will also be administered. Cognitive and behavioral assessments should not be administered while participants are fasting or immediately after the LP procedure. At study visits during which fasting samples are collected on the same day that cognitive assessments are administered, a break and food should be given to participants in between the fasting procedure and cognitive and behavioral assessments.

The optional lumbar puncture should be performed in the morning after an overnight fast, if possible. CSF samples will be used to measure levels of Abeta42, Abeta40, total tau, phospho-tau181, insulin, F2-Isoprostanes, cytokines, and BDNF. Additionally, CSF sample will be banked for future exploratory analysis. CSF will be collected and immediately frozen upright on dry ice for at least 20 minutes before being packaged along with the frozen plasma to be shipped overnight frozen on dry ice to the central biomarker laboratory.. Site staff will call the participant within approximately 24 hours from the lumbar puncture procedure to inquire about the participant's well being and possible adverse events.

Participants who continue to meet all protocol inclusion and exclusion criteria will be randomized to receive either insulin or placebo for the next 12 months, plus 6 month of open-label. All Baseline study procedures should occur before the start of the administration of any study drug.

Participants and study partners will be trained on how to appropriately use the intranasal device utilizing a test dose of placebo and shown how to record information in the study diary. The participant and study partner will be instructed to bring any unused study drug and their study diary to the clinic at each study visit (Month 3, 6, 9, 12, 15, 18) so that study staff can assess study drug compliance.

#### **7.4 Month 3 (Visit 3)**

The Month 3 visit is scheduled three months (+/- 2 weeks) from day one of the Baseline visit. At the Month 3 visit, the ADAS-Cog12 will be administered. The Research Satisfaction Survey will also be administered. Additionally, vital signs and weight will be obtained, a nasal examination will be conducted, adverse events and concurrent medications will be recorded. Participants will bring their device, study diary and any used and unused study drug vials to the site. Study drug compliance will be assessed. POD components (actuators, vial adapters, canisters and POD tips) will be dispensed..

#### **7.5 Month 6 (Visit 4)**

The Month 6 visit is scheduled six months (+/- 2 weeks) from day one of the Baseline visit. At the Month 6 visit, blood for plasma biomarkers will be collected. Plasma insulin, glucose, A $\beta$ 40 and A $\beta$ 42 should be measured in the morning after an overnight fast, if possible.. Additional plasma, along with serum and peripheral blood mononuclear cells (PBMCs) will be collected and banked. Samples will be shipped frozen to the central biomarker laboratory where the samples will be analyzed and banked. Additional blood for clinical laboratory evaluations will be conducted to monitor safety and tolerability.

Cognitive and behavioral assessments will be performed (during non fasting session). The study procedures will be standardized such that the ADAS-Cog12 will be the first cognitive assessment administered. Additional assessments include the MMSE, memory composite (Story Recall and FCSRT), an executive function test (Trail-making Test), CDR-SB, the ADCS-ADL-MCI and NPI. The Research Satisfaction Survey will also be administered.

In addition, vital signs and weight will be obtained, physical, neurological and nasal examinations will be conducted, adverse events and concurrent medications will be recorded.. Participants will bring their device, study diary and any used and unused study drug vials to the site. Study drug compliance will be assessed. POD components (actuators, vial adapters, canisters and POD tips) will be dispensed.

#### **7.6 Month 9 (Visit 5)**

The Month 9 visit is scheduled nine months (+/- 2 weeks) from day one of the Baseline visit. At the Month 9 visit, the ADAS-Cog12 will be administered. In addition, vital signs and weight will be obtained, a nasal examination will be conducted, adverse events and concurrent medications will be recorded. Participants will bring their device, study diary and any used and unused study

drug vials to the site . Study drug compliance will be assessed. POD components (actuators, vial adapters, canisters and POD tips) will be dispensed.

### **7.7 Month 12 (Visit 6)**

The Month 12 visit is scheduled 12 months (+/- 2 weeks) from day one of the Baseline visit. Month 12 visit is the last visit before the 6-month open-label period and the visit may occur over multiple days. The MRI should be conducted prior to the LP.

Blood for plasma biomarkers will be collected immediately before participants undergo the optional lumbar puncture. Plasma insulin, glucose, A $\beta$ 40 and A $\beta$ 42 should be measured in the morning after an overnight fast, if possible. Additional plasma, along with serum and peripheral blood mononuclear cells (PBMCs) will be collected and banked. Clinical laboratory evaluations will be conducted to monitor safety and tolerability.

The optional lumbar puncture should be performed in the morning after an overnight fast, if possible. Additionally, CSF sample will be banked for future exploratory analysis. CSF will be collected and immediately frozen upright on dry ice for at least 20 minutes before being packaged along with the frozen plasma to be shipped overnight frozen on dry ice to the central biomarker laboratory. Site staff will call the participant within approximately 24 hours from the LP procedure to inquire about the participant's well being and possible adverse events.

Cognitive and behavioral assessments will be performed. The study procedures will be standardized such that the ADAS-Cog12 will be the first cognitive test administered. Additional assessments include the MMSE, a memory composite (Story Recall and FCSRT), Trail-making Test A and B, the CDR-SB, the ADCS-ADL-MCI and the NPI. The Treatment Blinding Questionnaire and the Research Satisfaction Survey will also be administered. Cognitive and behavioral assessments should not be administered while participants are fasting or immediately after the LP procedure.

In addition, vital signs and weight will be obtained, physical, neurological and nasal examinations will be conducted, adverse events and concurrent medications will be recorded. Participants will bring their device components, study diary and any used and unused study drug vials to the site. Study drug compliance will be assessed. POD components (actuators, vial adapters, canisters and POD tips) will be dispensed.

Participants who were previously taking placebo will cross over to active study drug. All participants will receive the active study drug during the six-month open-label period.

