### 2.2.1 Intranasal Pathways to the CNS

Olfactory sensory neurons are directly exposed to the external environment in the upper nasal cavity while their axons extend through the cribriform plate to the olfactory bulb. Following intranasal administration, drugs can be directly transported to the CNS, bypassing the periphery. Several extraneuronal and intraneuronal pathways from the nasal cavity to the CNS are possible. The extraneuronal pathways appear to rely on bulk flow transport through perineural channels to the brain or CSF. In recent studies, labeled INI or a closely related peptide, insulin-like growth factor-I (IGF-I), were administered to rodents (Thorne, Pronk et al. 2004; Francis, Martinez et al. 2008). Within 30 minutes, signal was detected along olfactory and trigeminal channels, as well as in the hippocampus, amygdala and rostral and caudal cortex. An additional extracellular pathway was identified with quick access to the CSF after absorption into the submucosa along the olfactory nerve and cribriform plate (Born, Lange et al. 2002; Frey 2002; Thorne, Pronk et al. 2004). These extracellular pathways provide direct access to the CNS within minutes of intranasal administration. Additionally, an intraneuronal pathway delivers drugs to the CNS hours or days later (Broadwell and Balin 1985; Shipley 1985; Baker and Spencer 1986; Balin, Broadwell et al. 1986). Viruses and microorganisms (Fairbrother and Hurst 1930; Faber 1938; Bodian and Howe 1941), amino acids (Weiss and Holland 1967), and proteins (Kristensson and Olsson 1971; Shipley 1985; Thorne, Emory et al. 1995) can also enter the CNS via nasal routes. In particular, substances with lower molecular weights are more likely to be transported to the CNS along intranasal pathways (Sakane, Akizuki et al. 1995). Insulin's molecular weight of about 5800 g/mol makes it a good candidate for intranasal delivery. Animal studies show labeled uptake to hippocampus and rostral and caudal cortex following INI administration (Francis, Martinez et al. 2008). In a murine diabetes model, INI reduced brain atrophy, while increasing synaptic markers and activation of Akt, CREB, and GSK3 $\beta$ . Memory enhancement was also observed on Water Maze and radial arm tasks (Francis, Martinez et al. 2008). Human functional and cognitive studies of INI also support insulin's transport to the CNS. INI treatment increases CSF insulin levels and induces changes in auditory-evoked brain potentials compared to placebo (Kern, Born et al. 1999). INI improves verbal memory acutely in persons with AD and aMCI without affecting plasma insulin or glucose levels at the dose included in the study (Reger, Watson et al. 2006). Regarding chronic effects, several studies reported that 2 months of daily insulin administration (160 IU/day) significantly improves verbal memory in young healthy adults (Benedict, Hallschmid et al. 2004; Stockhorst, de Fries et al. 2004; Benedict, Kern et al. 2008; Hallschmid, Benedict et al. 2008; Stockhorst, de Fries et al. Submitted for publication). Finally, Section 3.0 presents results in a preliminary study in which insulin was administered to adults with AD or aMCI for 4 months.

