## 8.0 EARLY TREATMENT/STUDY DISCONTINUATION

The investigators at each site will make every reasonable effort to maximize participant retention. However, if an investigator removes a participant from treatment or study, or if a participant declines further treatment or study participation, an Early Discontinuation Visit will be completed as soon as possible following discontinuation of the study drug and or at time of study discontinuation. The Early Discontinuation Visit will contain the same assessments as the Month 12 visit, to allow collection of the main outcome measures. Depending on when the last LP or MRI was conducted, certain procedures may not be required at the Early Discontinuation Visit. If an in-person visit is not possible, site personnel will complete as much of the Early Discontinuation Visit as possible by telephone. All early treatment discontinuation participants will be strongly encouraged to complete all remaining visits through Month 12 visit.

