7.2 Visit Windows

As subjects do not always adhere to the protocol visit schedule, the following rules are applied to assign actual visits to analysis visits. Listed below are the visit windows and the target days for each visit. The reference day is Study Day 1. If a subject has 2 or more actual visits in one visit window, the visit closest to the target day will be used as the protocol visit for that visit window. Listed below (Table 2) are the visit windows and the target days for each visit defined in the protocol.

Table 2: Visit Windows for Analysis

Visit Code	Time Interval (days)	Target (days)
bl	(-30, 1)	1
m03	(2, 136)	91
m06	(137, 225)	181
m09	(226, 315)	271
m12	(316, 379)	366
m15	(380, 502)	458
m18	(503, 554)	541

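### SAP 7.2 picks the Month 12 value by study day alone, so a post-crossover assessment can replace a blinded one and a blinded Day 380 visit drops out of the primary contrast

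*Protocol*

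**What the plan says.** **Intended order.** Protocol 7.7 states "Month 12 visit is the last visit before the 6-month open-label period and the visit may occur over multiple days". It sets the timing as "The Month 12 visit is scheduled 12 months (+/- 2 weeks) from day one of the Baseline visit", and its last paragraph says "Participants who were previously taking placebo will cross over to active study drug". Protocol 15.3 likewise puts open-label treatment after 12 months of double-blind treatment. SAP 5.2 limits the blinded-phase analysis to visits up to and including 12 months.

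**What Baseline has and Month 12 lacks.** Protocol 7.3 allows seven days for the Baseline assessments and adds "All Baseline study procedures should occur before the start of the administration of any study drug". Section 7.7 puts no limit on the length of the Month 12 visit and has no matching sentence about the first open-label dose.

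**How the data are assigned.** SAP 7.2 uses study-day windows: m12 is Days 316-379 with target 366, and m15 is Days 380-502 with target 458. Then: "If a subject has 2 or more actual visits in one visit window, the visit closest to the target day will be used". Neither the windows nor this rule mentions crossover or treatment phase.

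**A possible second assessment.** Protocol 8.0: "The Early Discontinuation Visit will contain the same assessments as the Month 12 visit". The only waiver it describes depends on when the last lumbar puncture or MRI was done.

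**The concern.** The primary null hypothesis (SAP 7.4) concerns the ADAS-Cog12 difference at month 12, and SAP 7.2 decides which value fills that cell. Crossover happens on a different study day for each participant, so a fixed cut-off at Day 379 can misclassify in both directions. A value obtained on open-label insulin can be analysed as a placebo Month 12 value, and a properly blinded Month 12 value can be pushed into m15.

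The first error changes treatment only for placebo participants, because the active arm is on insulin either way. If insulin works, it pulls the arms together. The protocol itself gives a reason to expect some early effect: "INI improves verbal memory acutely in persons with AD and aMCI". Ratings after crossover would also be made knowing that the participant receives insulin. The second error loses primary-endpoint data from a visit that was on time.

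**Working it through.** **Inputs.** Month 12 timing: 12 months ± 14 days (Protocol 7.7). Windows, targets and the nearest-visit rule: SAP 7.2, Table 2. SD 5.72, differences of 1.6-2.6 points and dropout of 0.15-0.25: Protocol 12.1. Total of 240-300, allocated 1:1: Protocol 5.1 and 15.3. Two-sided 0.05: SAP 6.2.

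**Step 1: put both documents on one scale.** I take Study Day 1 as day one of the Baseline visit, so 12 months is Day 366, the SAP target. The protocol then allows 366 ± 14 = Days 352-380. The scheduled Month 15 visit is 458 ± 14 = Days 444-472, which cannot fall in m12. A post-crossover value in m12 therefore needs an extra assessment.

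**Step 2: when does a later value replace the blinded one?** Let the blinded visit be on Day v < 366, with distance k = 366 − v. A later assessment wins if it is less than k days from Day 366 and still inside m12, that is, on Days v + 1 to min(366 + k − 1, 379).

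| Blinded visit | Distance from 366 | Later days still in m12 | Days that replace it |
|---|---|---|---|
| 352 | 14 | 353-379 (27) | 353-379 (27) |
| 359 | 7 | 360-379 (20) | 360-372 (13) |
| 366 | 0 | 367-379 (13) | none |
| 373 | 7 | 374-379 (6) | none |

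Example: a placebo participant is tested on Day 352, crosses over, stops treatment and has an Early Discontinuation Visit on Day 364. The distances are 14 and 2 days, so the open-label value becomes m12.

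**Step 3: the upper edge.** The last permitted day is 366 + 14 = 380, but m12 ends on Day 379. A blinded visit on Day 380 is therefore m15. A Month 15 visit on, say, Day 458 is 0 days from that target, against 458 − 380 = 78 days, so the Day 380 value is discarded. Without a nearer visit it is analysed as m15. Either way the Month 12 cell is empty.

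**Step 4: possible size of the first error.** The documents give no frequency, so this is illustration only.

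First, the plan's own figure. At a difference of 2.2, n per arm = 2 × (5.72 × (1.960 + 0.842) / 2.2)² = 106.1, or 212.2 in total. Multiplied by 1 + 0.15/2, this gives 228.2, matching the 228 in Protocol Table 5. The entry reproduces as a total, although the text calls it per arm. That does not affect the present point.

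Now let a fraction f of placebo m12 values be post-crossover, each carrying a share g of the full effect. The difference becomes 2.2 × (1 − f·g). With 240 randomised and 15% dropout (102 per arm), SE = 5.72 × √(2/102) = 0.801.

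| f | g | Difference | Power |
|---|---|---|---|
| 0 | – | 2.20 | 0.784 |
| 0.05 | 0.25 | 2.17 | 0.774 |
| 0.10 | 0.50 | 2.09 | 0.742 |
| 0.20 | 1.00 | 1.76 | 0.594 |

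The last row is an extreme: it credits the whole 12-month effect to at most 27 days of exposure after an in-window visit.

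**The case against.** The strongest reply is that the order is already fixed. Protocol 7.7 and 15.3 both place Month 12 before open label. Within that visit "the ADAS-Cog12 will be the first cognitive test administered", and Protocol 15.0 has participants skip the morning dose on visit days to avoid acute insulin effects. A participant with one ADAS-Cog12 before crossover and no further assessment in the window is not contaminated. Replacement needs an early visit, crossover, a prompt stop and a repeated battery. An Early Discontinuation Visit exists to collect the main outcomes, which would just have been collected.

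All of this stands, and it limits how often the first error can occur. It does not change the rule, which still selects the wrong value when the sequence happens. The data limit in SAP 5.2 does not help, because SAP 7.2 defines which visit counts as month 12.

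A reader might infer more than the documents support:
- *That nothing places Month 12 before crossover.* The protocol does so; what is missing is a rule in the data based on the dose date.
- *That a multi-day visit lets an open-label dose fall between Month 12 assessments.* Section 7.7 does not rule this out in terms, but such a dose would contradict its stated order.
- *That late blinded values generally enter the Month 18 model.* They do so only when no visit is nearer Day 458.
- *That MRI and CSF results are affected in the same way.* SAP 7.7 models them with continuous time, so the nearest-visit mechanism is not shown to apply.

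**Conclusion.** The point holds as a defect in the SAP 7.2 assignment rule. The rule ignores treatment phase, so it can replace a blinded Month 12 ADAS-Cog12 with a post-crossover one when the blinded visit precedes Day 366, and it removes an on-time blinded visit on Day 380 from the primary contrast.

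The expected effect is small. The first error needs an unscheduled or discontinuation assessment within at most 27 days of an in-window visit. The second affects one day of the permitted range, plus any blinded visit later than that. Under the milder assumptions above, power falls from 0.784 to between 0.774 and 0.742. These fractions are assumptions, and dilution presumes that insulin has a benefit.

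The Day 380 result rests on Study Day 1 being day one of Baseline. If Study Day 1 were a later Baseline day, the last permitted day would move to 379 or earlier; a leap day would move it to 381. SAP 7.2 does not define Study Day 1 further.

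**What to change.** **SAP 7.2: assign phase before window.**
- Only assessments made before the first open-label dose may be m12. If both fall on one date, use recorded times or treat the assessment as first, in line with Protocol 7.7.
- A pre-crossover Month 12 visit stays m12 even after Day 379, at least to the end of the protocol window.
- m15 and m18 accept only post-crossover values.
- Define Study Day 1, and say how participants who never start open-label drug are handled, since they have no dose date.

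**Data collection.** Record the date of the first open-label dose.

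**Protocol 7.7.** Add a sentence parallel to the one in 7.3, stating that Month 12 outcome assessments are completed before open-label drug starts. This makes explicit an order that 7.7 and 15.3 already imply.

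**Cost.** One date field, one SAP rule and one protocol sentence. Open-label supply may start a few days later when the Month 12 visit spans several days.
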